7 ASSESSMENTS AND METHODS

7.1 Demographic and Baseline Information

Demographic and baseline information will be recorded during the Screening Visit.

7.1.1 Demographic and Baseline Characteristics

Demographic and baseline characteristics are sex, age, race and ethnic origin, height, weight, calculated BMI, and ABO Rhesus blood type.

7.1.2 Medical History

Medical history (conditions and surgical treatment) will be obtained by patient interview. Records of past diseases and treatments (eg, hospital discharge letters) will be obtained for the study files, if available. Any untoward medical events that occur from the time/date of informed consent signature until the first Study SCGAM-06 specified CUTAQUIG dose will be recorded as medical history.

7.1.3 Prior and Concomitant Medication Use

Prior and concomitant medications and therapies will be obtained by patient interview. See Section 4.2 for details on prior and concomitant medication collections.

7.1.4 Documentation of Previous SCIG Treatment and IgG Trough Levels

Documentation of consistent or stable doses of SCIG treatment will be collected from patients' medical records.

Documentation of IgG trough levels will be collected from pre-study laboratory results obtained prior to enrollment; 2 prior IgG trough levels are required within 1 year of Screening, with 1 trough level obtained within 3 months prior to enrollment. If no prior IgG trough level is available within 3 months prior to Screening, the Screening IgG trough level may be used as the 2nd reading.

7.2 Efficacy Assessments

To study the effectiveness of CUTAQUIG to maintain total IgG trough levels when administered every other week, in the prevention of infections, and changes in patient QoL assessments, the following measurements will be recorded and efficacy parameters assessed, throughout the study:

- Change in IgG trough levels when switched from every week to every other week administration (Cohort 3) (See Section 7.4.1)
- Number of episodes of SBI, per person-year on treatment, along with type and severity of infection, and time to resolution
- Number of episodes of any other infections (including acute sinusitis, exacerbation of chronic sinusitis, acute otitis media, acute bronchitis, infectious diarrhea etc.), along with type and severity of infection, and time to resolution
- Number of days of use and annual rate of antibiotics (oral, parenteral, oral plus parenteral, prophylactic and therapeutic), along with type and dosage of antibiotic

- QoL assessments (See Section 7.4.2)

For data collection of bacterial infections, in addition to on-site AE assessments, each patient will be provided with an individual diary to be completed by the patient during the home therapy time. The patient's diary will be checked for accuracy of the data by the Investigator and collected at each study visit. The data will be then transferred into the eCRF. A new diary will be handed out to the patient for the following period until the next infusion visit at the site.

For the purpose of this study the following events will be considered as SBIs, to be included in the primary efficacy analysis:

- Bacterial pneumonia
- Bacteremia/sepsis
- Osteomyelitis/septic arthritis
- Visceral abscess
- Bacterial meningitis

The presence of any of these infections should be verified by the specific differentiated diagnostic examinations [25] given in Table 8.

Table 8: Diagnostic Criteria for Serious Bacterial Infection Types

Infection: Bacteremia/sepsis ^a

 • Symptoms: chills, rigors. • Physical findings: fever, hypothermia, tachycardia, tachypnea, hypocarbia, hypotension (systolic blood pressure <90 mm Hg or a reduction of >40 mm Hg from baseline in the absence of other causes of hypotension), altered mental status, petechiae, purpura, oliguria, cutaneous vasodilation/vasoconstriction. • Laboratory tests: positive blood culture^b, leukocytosis (white blood cell (WBC) count >12,000/mm³), differential WBC count demonstrating >10% immature (band) neutrophils, leukopenia, thrombocytopenia, coagulopathy, lactic acidosis.
Infection: Bacterial Meningitis

 • Symptoms: headache, stiff neck, mental status changes, irritability, decreased feeding (infants), photophobia, nausea/vomiting, rigors, seizures. • Physical findings: Kernig's sign, Brudzinski's sign, meningococcal rash, fever of >38°C oral or >39°C rectal. • Laboratory tests: positive cerebrospinal fluid (CSF) Gram stain and/or culture and/or positive CSF bacterial antigen assay, positive blood culture^c, CSF leukocytosis with neutrophil predominance, decrease in CSF glucose.
Infection: Osteomyelitis/Septic Arthritis

 • Symptoms: pain, decreased range of motion, tenderness, edema, redness, warmth over the involved site (local inflammatory symptoms/signs may be lacking in adults).

- **Physical findings:** evidence of soft tissue infection adjacent to the involved bone/joint, drainage from sinus tract from involved bone, fever of $>38^{\circ}\text{C}$ oral or $>39^{\circ}\text{C}$ rectal.
- **Laboratory tests:** positive blood culture, positive probe to bone, positive bone aspirate culture, positive bone biopsy culture, positive bone histopathology, positive joint fluid Gram stain and culture.
- **Imaging studies:** **positive X-ray, nuclear medicine bone scan, magnetic resonance imaging scan, or computed tomography scan showing bony destruction with radiolucent areas; for chronic osteomyelitis: sequestra, involucra.**

Infection: Bacterial Pneumonia^d

- **Symptoms:** productive cough/change in character of sputum, dyspnea or tachypnea, chills, chest pain, rigors, headache, fatigue, sweats, anorexia, myalgia.
- **Physical findings:** rales; pulmonary consolidation as reflected by: dullness on percussion, bronchial breath sounds, egophony; fever $>38^{\circ}\text{C}$ oral or $>39^{\circ}\text{C}$ rectal, or $<36^{\circ}\text{C}$, hypothermia (temperature $<36^{\circ}\text{C}$ oral or $<37^{\circ}\text{C}$ rectal).
- **Laboratory tests:** leukocytosis, differential WBC count of $>10\%$ band neutrophils, leukopenia, hypoxemia ($\text{PaO}_2 <60$ mm Hg on room air), positive blood culture, Gram stain and culture of deep expectorated sputum e, positive culture with or without positive Gram stain of transtracheal aspirate, pleural fluid culture, lung biopsy, bronchoscopy with bronchoalveolar lavage or protected brush sampling.
- **Imaging studies:** **Pulmonary infiltrate with consolidation on chest X-ray (new in comparison with baseline chest X-ray)**

Infection: Visceral Abscess

- **Symptoms:** abdominal pain, anorexia, weight loss, cough/pleuritic chest pain (hepatic abscess), rigors (seldom present).
- **Physical findings:** intermittent fevers (temperature $>38^{\circ}\text{C}$ oral or $>39^{\circ}\text{C}$ rectal), abdominal tenderness, palpable mass, hepatomegaly, jaundice.
- **Laboratory tests:** **positive Gram stain and/or culture from the infected site, with isolation of an appropriate pathogen**, positive blood culture, leukocytosis with accompanying left shift, differential WBC count of $>10\%$ immature (band) neutrophils, elevated serum amylase concentration (pancreatic abscess), elevated alkaline phosphatase concentration (hepatic abscess) pyuria in renal abscess.
- **Imaging studies:** **typical findings on ultrasound, computed tomography scan, magnetic resonance imaging scan, or radionuclide scan**

Notes to Table 8:

Items in bold are considered essential diagnostic features.

- a. Two of the following should be present to make the diagnosis of sepsis in adults: temperature $>38^{\circ}\text{C}$ oral/ $>39^{\circ}\text{C}$ rectal or $<36^{\circ}\text{C}$ oral or $<37^{\circ}\text{C}$ rectal; heart rate >90 beats/min; respiratory rate >20 breaths/min, or $\text{PaCO}_2 <32$ mm Hg; WBC count $>12,000/\text{mm}^3$, $<4,000/\text{mm}^3$, or $>10\%$ immature (band) forms. For pediatric patients, the definition of sepsis using age-specific criteria as

recommended by the International Consensus Conference on Pediatric Sepsis should be employed.[26]

- b. Indwelling catheter- or vascular access device-related blood-borne infections are not included because evidence is lacking that these are preventable with IVIG replacement therapy. For patients without indwelling catheters or vascular access devices, a single blood culture positive for a pathogenic organism will meet the diagnostic criteria for bacteremia. Patients meeting criteria for positive blood culture but without 2 or more of the sepsis criteria listed above will be classified as having bacteremia.
- c. A blood culture positive for growth of *Streptococcus pneumoniae*, *Neisseria meningitidis*, or *Haemophilus influenzae*, in combination with CSF leukocytosis and/or decrease in CSF glucose, can serve to confirm the diagnosis of acute bacterial meningitis.
- d. For the diagnosis of pneumonia in adults, commonly at least 2 of the listed symptoms and/or signs should be present in conjunction with at least one laboratory and one imaging studies diagnostic element. However, for the purposes of counting serious bacterial infection episodes in a clinical trial of IVIG, the finding of a new pulmonary infiltrate with consolidation on chest X-ray is considered sufficient. To establish the diagnosis of bacterial pneumonia for pediatric patients, most of the same diagnostic criteria listed may be used, with the following exceptions: Because pediatric patients may not produce a sputum specimen for culture, blood cultures or serology may be substituted to identify the etiologic bacterial pathogen. In infants age 3 to 24 months, who tend to have a higher baseline temperature, fever is defined as a rectal temperature $>38.3^{\circ}\text{C}$ (101°F). In children >2 years, fever is more commonly defined as a rectal temperature $>38^{\circ}\text{C}$ (100.4°F). In pediatric patients, elevations of WBC counts $>15,000/\text{mm}^3$ are frequent but could be variable in patients with bacterial pneumonia, or leukopenia with WBC count $<5000/\text{mm}^3$ may be observed, usually associated with severe infection.
- e. It is recommended to obtain a deep expectorated sputum gram stain to demonstrate the presence of microorganisms on examination of 10-20 oil immersion microscopic fields and <10 squamous epithelial cells and >25 polymorphonuclear leukocytes at 10X low power magnification to determine suitability of sputum culture.

7.3 Safety Assessments

The following safety assessments shall be collected:

- Adverse events (AEs) and serious adverse events (SAEs) temporally associated with the administration of IMP (for definitions and reporting requirements, see Section 7.3.1 for AEs and Section 7.3.3 for SAEs)
- Pregnancies (Section 7.3.8.2)

7.3.1 Adverse Events

7.3.1.1 Definitions

Adverse event (AE): An AE is any untoward medical occurrence in a study patient receiving an IMP and which does not necessarily have a causal relationship with this treatment. An AE can therefore be any unfavorable and unintended sign (including an abnormal laboratory finding), symptom, or disease temporally associated with the use of an IMP, whether or not related to the IMP.

An AE is defined as treatment-emergent (TEAE) if the event began or worsened after the start of first infusion of trial medication. For patients in this study, “treatment-emergent” will refer to events with onset date/time after the start of the first CUTAQUIG infusion at the Stabilization Period Week 0 Visit.

Adverse drug reaction (ADR): An ADR is any noxious and unintended response to an IMP related to any dose. The phrase “response to an IMP” means that a causal relationship between the IMP and an AE carries at least a reasonable possibility (ie, the relationship cannot be ruled out).

Other Significant AEs: Any non-serious AE or marked laboratory abnormality that results in:

- withdrawal of IMP treatment
- and/or dose reduction
- and/or initiation of significant additional concomitant therapy (ie, medications given intravenously)

Withdrawal due to AE/ADR: AE/ADR leading to discontinuation of treatment with IMP. Any such events will be followed up by the Investigator until the event is resolved or until the medical condition of the patient is stable. All follow-up information collected will be made available to the Sponsor.

7.3.1.2 Collection

The condition of the patient will be monitored throughout the study. At each visit, whether scheduled or unscheduled, AEs will be elicited using a standard non-leading question such as “How have you been since the last visit/during the previous study period?” In addition, patient diaries (if applicable) will be checked by the Investigator for any documented event.

Any AE which occurs during the study from the time/date of first dose of CUTAQUIG through the Termination Visit will be noted in detail on the appropriate pages of the eCRF. Any untoward medical events that occur from the time/date of informed consent signature until the first CUTAQUIG dose will be recorded as medical history. If the patient reports several signs or symptoms representing one syndrome or diagnosis, the diagnosis should be recorded in the eCRF. The Investigator will grade the severity of all AEs (mild, moderate or severe), the seriousness (non-serious or serious), and causality, as defined below (Section 7.3.1.3, Section 7.3.3, and Section 7.3.1.4, respectively). The Sponsor is also responsible to assess the expectedness of each ADR (expected or unexpected), as defined below (Section 7.3.1.5).

In the event of clinically significant abnormal laboratory findings, the tests will be confirmed and followed-up until they have returned to normal and/or an adequate explanation is available.

Diseases, signs and symptoms and/or laboratory abnormalities already existing before the first administration of IMP are not considered as AEs when observed at a later stage unless they represent an exacerbation in intensity or frequency (worsening).

The Investigator should always provide detailed information concerning any abnormalities and the nature of, and reasons for, any necessary action(s), as well as any other observations or comments which are useful for the interpretation and understanding of patients’ AEs.

7.3.1.3 Severity

The intensity/severity of AEs will be graded as follows:

- **Mild:** an AE, usually transient, which causes discomfort but does not interfere with the patient's routine activities
- **Moderate:** an AE which is sufficiently discomforting to interfere with the patient's routine activities
- **Severe:** an AE which is incapacitating and prevents the pursuit of the patient's routine activities

The severity grading of an AE is up to the medical judgement of the Investigator and will be decided on a case-by-case basis.

7.3.1.4 Causality

The relationship of AEs to the administered IMP will be assessed by the Investigator:

- **Probable:** reports including good reasons and sufficient documentation to assume a causal relationship, in the sense of plausible, conceivable, likely, but not necessarily highly probable. A reaction that follows a reasonable temporal sequence from administration of the IMP; or that follows a known or expected response pattern to the suspected medicine; or that is confirmed by stopping or reducing the dosage of the medicine and that could not reasonably be explained by known characteristics of the patient's clinical state.
- **Possible:** reports containing sufficient information to accept the possibility of a causal relationship, in the sense of not impossible and not unlikely, although the connection is uncertain or doubtful, for example because of missing data or insufficient evidence. A reaction that follows a reasonable temporal sequence from administration of the IMP; that follows a known or expected response pattern to the suspected medicine; but that could readily have been produced by a number of other factors
- **Unlikely:** reports not following a reasonable temporal sequence from IMP administration. An event which may have been produced by the patient's clinical state or by environmental factors or other therapies administered.
- **Not related (unrelated):** events for which sufficient information exists to conclude that the etiology is unrelated to the IMP.
- **Unclassified:** reports which for one reason or another are not yet assessable, eg, because of outstanding information (can only be a temporary assessment). Sites are encouraged not to use this category unless necessary, as it will be assumed there is a causal relationship and may lead to premature fulfillment of Suspected Unexpected Serious Adverse Reaction (SUSAR) criteria.

7.3.1.5 Classification of ADRs by Expectedness

ADRs will be classified by the Sponsor as either expected or unexpected:

- **Expected:** an ADR that is listed in the current edition of the Investigator's Brochure or other reference safety information.

- **Unexpected:** an ADR that is not listed in the current edition of the Investigator's Brochure or other reference safety information, or that differs because of greater severity or greater specificity.

7.3.1.6 Outcome of AEs

Outcome of all reported AEs will be documented as follows:

- Recovered, resolved
- Recovering, resolving
- Not recovered, not resolved
- Recovered, resolved with sequelae
- Fatal
- Unknown

NOTE: A patient's **death** per se is not an event, but an outcome. The event which resulted in the patient's death must be fully documented and reported, even in case the death occurs within 4 weeks after IMP treatment end and regardless of whether or not it is considered treatment-related.

7.3.1.7 Action(s) taken

AEs requiring action or therapy must be treated with recognized standards of medical care to protect the health and well-being of the patient. Appropriate resuscitation equipment and medicines must be available to ensure the best possible treatment in an emergency situation.

The action taken by the Investigator must be documented:

a) General actions taken in the event of an AE

- None
- Medication (other than IMP) or other (eg, physical) therapy started
- Test performed
- Other (to be specified)

b) IMP-related actions taken in the event of an AE

- None
- Product withdrawn
- Dose reduced
- Dose increased

The Investigator will follow up on each AE until it has resolved or until the medical condition of the patient is stable, and all relevant follow-up information will be reported to the Sponsor.

7.3.2 Local Site Reactions

Local infusion-site reactions will be assessed by both patients and investigators.

Patients will grade the overall perception of local reactions in their diaries after each infusion using a 4-point rating scale: 0=none, 1=mild, 2=moderate, 3=severe.

Investigators will evaluate local reactions after infusion at every study visit, using a 4-point rating scale: 0=none, 1=mild, 2=moderate, 3=severe.

The following observations must not be reported as local infusion site reactions as all of these can be expected in all patients:

- Local mass (usually reported as "swelling") caused by the injected CUTAQUIG volume
- Small blood drops at the infusion site caused by the needle sticks
- Short and immediate pain at the infusion site caused by the puncture itself

Any other local infusion site reactions such as redness, pain (other than the pain caused by the puncture itself), pruritus, rash or other skin reactions, bleedings (other than small blood drops caused by the needle stick), local thrombosis, induration or swellings (caused by other grounds than the injected volume) must be reported on the adverse events page in the eCRF.

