3 INVESTIGATIONAL PLAN

3.1 Primary and Secondary Endpoints

3.1.1 Primary Endpoints

There is no single primary endpoint in this study. The co-primary objectives are to compare total IgG trough levels from weekly infusions to every other week infusions and to assess safety and tolerability of increased infusion volumes and increased infusion rates at each infusion site and every other week dosing. These will be assessed using the following variables:

- Change in individual total IgG trough levels from weekly infusions to every other week infusions (Cohort 3)
- Occurrence of treatment-emergent AEs (TEAEs) throughout the entire Stabilization and Treatment Periods starting with the first infusion of IMP
- Occurrence of TEAEs temporally associated with CUTAQUIG delivered during the Treatment Period
- Occurrence of TEAEs temporally associated with CUTAQUIG delivered during the Stabilization Period
- TEAEs by speed of infusion
- Local infusion-site reactions
- Laboratory parameters (hematology, clinical chemistry, urinalysis)

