6.1.3 CUTAQUIG Treatment Visits (Baseline [Week 0] through Week 24)

After completing the 4-week Stabilization Period (or Screening Visit for patients who are currently enrolled in Study SCGAM-03), patients will enter the Treatment Period

and begin their infusion parameters according to their corresponding cohort assignment (Section 3.3.2).

On study visit days, CUTAQUIG administration will be performed on site; otherwise, CUTAQUIG will be administered at home.

During the Treatment Period, the following on-site visits are required as specified below:

Cohort 1	Baseline, Weeks 4, 8, 12, and 24
Cohort 2	Baseline, Weeks 4, 8, 12, and 24
Cohort 3	Baseline, Weeks 4, 12, and 24

For Cohort 1 and Cohort 2, if a patient has reached their maximum achievable volume or flow rate per infusion site at Week 12, they do not need to complete remaining interim (4-week interval) on-site study visits at Week 16 and Week 20.

The following activities will be performed before on-site CUTAQUIG administrations:

- General physical examination (See Table 2 [Cohort 1], Table 3 [Cohort 2], and Table 4 [Cohort 3] for assessment schedules)
- Record body weight (all visits)
- Draw blood samples for total IgG trough level (See Table 9 for collection schedule)
- Draw blood samples for safety laboratory parameters (See Table 9 for collection schedule)
- Draw blood for serum retention samples, for patients who were previously enrolled in SCGAM-03 and did not participate in the Stabilization Period (Baseline Visit, only)
- Collect urine sample including sample for urine pregnancy test (females of childbearing potential, only) (See Table 9 for collection schedule)
- Collect vital signs (all visits)
- Complete QoL questionnaire (Baseline Visit, only)

The following activities will be performed during or after CUTAQUIG administration:

- Collect patient diary. The Investigator will review diary entries and query the patient about any AEs that may have occurred and any changes in concomitant therapies (medication and non-drug therapy). Any updates to concomitant medication use and adverse events will be recorded. Relevant diary data will be transferred to the eCRF. Discrepancies between patient diary entries and eCRF entries must be explained by the Investigator.
- Infusion of CUTAQUIG by the patient, according to cohort assignment (every visit – see Section 3.3.2 for dosing information)
- Assess patient infusion technique and, if necessary, re-train on proper administration

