3.2. Study Endpoints (Target Variables)

3.2.1. Primary Target Variables

The co-primary objectives are to compare total IgG trough levels from weekly infusions to every other week infusions and to assess safety and tolerability of increased infusion volumes and increased infusion rates at each infusion site and every other week dosing. These will be assessed using the following variables:

- Change in individual total IgG trough levels from weekly infusions to every other week infusions (Cohort 3)
- Occurrence of treatment-emergent AEs (TEAEs) throughout the entire Stabilization and Treatment Periods starting with the first infusion of IMP
- Occurrence of TEAEs temporally associated with CUTAQUIG delivered during the Treatment Period
- Occurrence of TEAEs temporally associated with CUTAQUIG delivered during the Stabilization Period
- TEAEs by speed of infusion
- Local infusion-site reactions
- Laboratory parameters (hematology, clinical chemistry, urinalysis)

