The safety analysis will comprise descriptive statistics, tabulations and listings of all TEAEs, safety laboratory results, vital signs and physical examination findings.

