10.1. Adverse Events

All reported AEs will be coded according to MedDRA.

An AE is defined as treatment-emergent, if first onset or worsening is after start of the first infusion of CUTAQUIG. Only treatment-emergent AEs (TEAEs) are accounted for in the analysis.

For each TEAE, the time relative to the start of the infusion will be calculated and the TEAE will be classified as temporally associated if the onset is during the infusion or within 72 hours after the end of the infusion.

All reported events will be listed and tabulated in full detail; in particular the following key statistics will be presented in a summary table:

- Total number of TEAEs reported.

Number of patients with

- Any TEAE
- Any drug related TEAE
- Any TEAE
- Any Drug Related TEAE
- Any Temporally Associated TEAE during Stabilization Period
- Any Temporally Associated TEAE during Treatment Period
- Any Local Site Reaction
- Any Severe TEAE
- Any Serious AE
- Product Withdrawn due to TEAE
- Study Discontinuation due to TEAE
- AE Outcome of Death

Also, the following TEAE tabulations of patient incidence will be presented:

- Temporally associated treatment-emergent adverse events during stabilization period by system organ class and preferred term
- Temporally associated treatment-emergent adverse events during treatment period by system organ class and preferred term
- Local site reaction treatment-emergent adverse events by system organ class and preferred term
- Treatment-emergent adverse events excluding local site reactions by system organ class and preferred term
- Serious treatment-emergent adverse events by system organ class and preferred term
- Serious treatment-emergent adverse events leading to study discontinuation by system organ class and preferred term
- Non-serious treatment-emergent adverse events by system organ class and preferred term
- Treatment-emergent adverse events leading to product withdrawal by system organ class and preferred term

- Treatment-emergent adverse events leading to early study discontinuation by system organ class and preferred term
- Treatment-emergent adverse events by highest relationship to treatment by system organ class and preferred term
- Treatment-emergent adverse events by maximum severity by system organ class and preferred term
- Infusion total flow rate and temporally associated treatment-emergent adverse events

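### The SAP specifies no summary of the 0-3 local-reaction grades, and its AE-based tables cannot cleanly show whether reactions per infusion change with the modified regimen

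*Protocol*

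**What the plan says.** Protocol 3.1.1 opens with "There is no single primary endpoint in this study" and then lists several variables, local infusion-site reactions among them. SAP 3.2.1 repeats the entry as "Local infusion-site reactions", without a scale, data source or summary measure.

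Protocol 7.3.2 sets up three routes for recording these reactions:

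- **Patient grade:** "Patients will grade the overall perception of local reactions in their diaries after each infusion using a 4-point rating scale", running from 0 (none) to 3 (severe).
- **Investigator grade:** "Investigators will evaluate local reactions after infusion at every study visit, using a 4-point rating scale", with the same levels.
- **AE page:** apart from three expected observations (a mass from the infused volume, small blood drops, brief puncture pain), local reactions "must be reported on the adverse events page in the eCRF".

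On data flow, Protocol 6.1.3 says "Relevant diary data will be transferred to the eCRF".

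SAP 10 describes its scope this way: "The safety analysis will comprise descriptive statistics, tabulations and listings of all TEAEs, safety laboratory results, vital signs and physical examination findings". Within SAP 10.1 the outputs specific to local reactions are:

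- a count of patients with any local site reaction;
- "Local site reaction treatment-emergent adverse events by system organ class and preferred term";
- two tables of total flow rate for local reactions, one of them by number of lines;
- a listing of local site reactions, source not stated.

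Other SAP outputs include local reactions without isolating them: treatment-emergent AE (TEAE) tables for temporally associated events, given separately for Stabilization and Treatment; the percentage of infusions with a temporally associated TEAE; and the per-patient ratio in SAP 10.2.

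**The concern.** The protocol plans a grade for every infusion on one scale, before and after the change of regimen. The SAP says in Section 2 that it covers all statistical analyses, yet it mentions neither grade nor the 4-point scale.

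The co-primary safety question is whether tolerability changes when volume per site, flow rate or dosing interval changes. It is best answered per infusion and per step. If the named outputs cannot answer it that way, a summary of the grades would have to be added after the data are seen. SAP 4.1 would then have it reported as an unplanned analysis in an open-label study. The SAP also leaves unclear which of the three records represents the endpoint.

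**Working it through.** The plan states no figure for this point, so there is none to reproduce. The check sets outputs against data and then tests whether the period-split tables compare like with like.

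**1. What each named output can show**

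| SAP output | Unit | Local reactions only? | Split by period? | By volume per site? |
|---|---|---|---|---|
| Count of patients with any local site reaction | patient | yes | no | no |
| Local-reaction table by class and term | patient | yes | no | no |
| Flow-rate and number-of-lines tables | flow rate / lines | yes | no | no |
| Listing of local reactions | record | yes | not stated | not stated |
| Temporally associated TEAEs by period | patient | no (local terms appear among others) | yes | no |
| Infusions with a temporally associated AE (SAP 10.1, 10.2) | infusion | no, all AEs pooled | no | no |

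No named tabulation combines a per-infusion unit, local reactions only, and a split by period or step.

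**2. Infusions per patient** (Protocol 3.3.2 and flow charts)

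- Stabilization: Weeks 0, 1, 2, 3 = 4.
- Cohorts 1 and 2, weekly from Baseline to Week 24: 25.
- Cohort 3, every other week from Baseline to Week 24: 13.

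**3. Planned grades** (minimum cohort sizes 15, 15 and 35; no dropout)

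- Patient grades: 30 × (4 + 25) + 35 × (4 + 13) = 870 + 595 = 1,465. If every patient skipped Stabilization: 30 × 25 + 35 × 13 = 1,205.
- Investigator grades, counting Stabilization Week 0, on-site treatment visits and Termination: 30 × 7 + 35 × 6 = 420 with required visits only; 30 × 9 + 35 × 6 = 480 with Weeks 16 and 20 attended; 30 × 6 + 35 × 5 = 355 with required visits only and no Stabilization.

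**4. Does the period-split patient count mislead?** Take a constant reaction rate p per infusion, so the regimen has no effect. With independent infusions, the chance of at least one reaction in n infusions is 1 − (1 − p)^n. The value p = 0.10 is illustrative; Protocol 1.1 cites reporting rates of 0.028 to 0.697 per infusion.

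- Stabilization, n = 4: 1 − 0.9^4 = 34%.
- Treatment, Cohort 3, n = 13: 1 − 0.9^13 = 75%.
- Treatment, Cohorts 1 and 2, n = 25: 1 − 0.9^25 = 93%.

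**5. Sensitivity to clustering.** SAP 10.2 says events within a patient cannot be assumed independent. Under a beta-binomial model with within-patient correlation ρ, the chance of no reaction is B(a, b + n) / B(a, b), where a = p(1/ρ − 1) and b = (1 − p)(1/ρ − 1). The values of ρ are assumptions.

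| p = 0.10 | n = 4 | n = 13 | n = 25 |
|---|---|---|---|
| independence | 34% | 75% | 93% |
| ρ = 0.1 | 30% | 58% | 72% |
| ρ = 0.3 | 24% | 39% | 47% |

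Clustering shrinks the spurious difference but does not remove it. At ρ = 0.3 incidence still goes from 24% to 39% or 47% with no change in the rate. A share of infusions has the same expected value, 10%, in both periods.

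**The case against.** **Generic commitments.** SAP 7 promises descriptive summaries of each primary variable, and Protocol 9.2 promises that all collected data will be listed and described by cohort. The listing of local reactions might contain grades, and the table list is in a separate document not available here. This stands as a limit: a reader might infer that the grades will go unused, and the documents do not support that. They show only that the SAP specifies no summary. The generic text names no grade, unit, step or rule for missing diary entries.

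**The AE route may capture the same reactions.** Protocol 7.3.2 sends local reactions to the AE page with no severity threshold, and AEs are graded mild, moderate or severe. Infusion counts are summarized under SAP 8.4, so reaction-free infusions could be derived. This stands. It would be tempting to call the AE record less sensitive, or the grades the only consistently scored data; neither is shown. The gap lies in the tabulations named.

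**Saturation.** One could argue that patient incidence is too near its ceiling to show an increase. For 25 independent infusions, raising p from 0.10 to 0.20 moves it only from 93% to 99.6%. But Cohort 3 has 13 infusions, where the move is from 75% to 95%, and with ρ of 0.1 to 0.3 the 25-infusion figures are 72% to 93% and 47% to 73%. The argument is fragile and is not relied on here.

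**Limits of the grades.** Patients entering directly from SCGAM-03 have no Stabilization Period. The investigator grade has only one Stabilization visit, Week 0. The diary item is an overall perception, and the protocol does not clearly say that patients leave out expected swelling from volume, which could rise by design in Cohort 1. Only relevant diary data go to the eCRF, and the diary contents in Protocol 5.7.2 do not mention the 0-3 grade. These points stand and shape the fix. They also argue against making the grades the primary summary.

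**Conclusion.** The concern holds in a limited form. The SAP specifies no summary of either 0-3 grade collected for a co-primary variable, and its named local-reaction outputs are AE-based, apart from a listing of unstated source. The period-split tables count patients over unequal numbers of infusions, the per-infusion ratio mixes local reactions with all other AEs, and no table relates reactions to volume per site, which is Cohort 1's question. The flow-rate and number-of-lines tables partly serve Cohort 2, but they too are built from TEAEs.

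For size: at a constant 0.10 per infusion the period-split tables would go from 34% to 75% (Cohort 3) or 93% (Cohorts 1 and 2) under independence, and from 24% to 39% or 47% at a correlation of 0.3, with no true change. These rest on the illustrative rate and the planned infusion counts without dropout.

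Local reactions are analysed descriptively with no decision rule, so no inference changes; the confirmatory test on IgG trough in Cohort 3 is untouched. The change should be made because it is cheap and bears on what the study can report about tolerability.

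**What to change.** Add to SAP 10.1, by cohort:

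- **Patient grade, per infusion:** the distribution over 0-3, and the shares of infusions graded 1 or higher and 2 or higher, for Stabilization and for each volume step (Cohort 1) or rate step (Cohort 2); for Cohort 3, the every-other-week period as a whole.
- **Within-patient change from Stabilization:** patient grade only, restricted to patients who had a Stabilization Period.
- **Investigator grade:** the distribution over 0-3 by visit.

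Present these alongside the AE tables, without requiring the grades to be the primary summary. State the source of the listing, how the grades relate to AE-page reactions, and how missing diary grades are handled. Confirm that the diary grade is transferred to the eCRF; if it is not, the patient-grade tables also need a data-transfer step.

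The cost is SAP wording and a few more descriptive tables. Some diary grades will be missing, so each table should show the number of infusions graded out of those given.
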